##### **11.4.3.1. Other Glucocorticoid Side Effects**

The management of common glucocorticoid side effects is well documented. Aggressive use of proton-pump inhibitors (PPIs), anti-hypertensives and other agents is strongly encouraged in order to maintain the use of dexamethasone in combination with selinexor in this study.

Patients with documented osteopenia or osteoporosis should continue to take dexamethasone with selinexor as indicated in the study. Standard precautions such as use of bisphosphonates should be instituted unless contraindicated.

#### **11.4.4. Concomitant Medication and Treatment**

Concomitant medication is defined as any prescription or over-the-counter preparation, including vitamins, dietary supplements, over-the-counter medications, and oral herbal preparations. Patients may continue their baseline medication(s). All concomitant medication(s) must be reported in the eCRF. Any diagnostic, therapeutic, or surgical procedure performed during the study period should be recorded, including the dates, description of the procedure(s), and any clinical findings, if applicable.

#### 11.4.4.1. Permitted Concomitant Medication

Patients will receive concomitant medications to treat symptoms, AEs, and intercurrent illnesses that are medically necessary as standard care. Medications to treat concomitant diseases like diabetes, hypertension, etc., are allowed.

#### 11.4.5. Restricted Medications

*Medications:* Although acetaminophen (paracetamol) use in combination with selinexor was restricted in previous selinexor studies based on theoretical interactions with glutathione (GSH), ongoing clinical safety evaluations on the use of these drugs together have not shown any significant clinical or laboratory abnormalities with doses of acetaminophen up to 1 gram and selinexor up to 55 mg/m^2 (approximately 80-100 mg). Therefore, there are no longer any restrictions on the use of acetaminophen or acetaminophen-containing products in combination with selinexor, EXCEPT on days of selinexor dosing, when acetaminophen must not exceed a total daily dose of 1 gram.

*Diet:* There are no dietary restrictions on this study. Patients should maintain adequate caloric and fluid intake.

#### 11.4.6. Prohibited Medications

*Concurrent therapies:*

Concurrent therapy with any non-study anticancer therapeutic is not allowed. Other investigational agents should not be used during the study. Use of any immunosuppressive agents during the study must be confirmed by the Medical Monitor.

*Medications:* Patients should not take glutathione (GSH)-, S-adenosylmethionine (SAM)-, or N-acetylcysteine (NAC)-containing products during this study as these products may enhance the metabolism of selinexor. Please see [Appendix 6](#) for a list of representative products. Patients must report all prescription and non-prescription medicines to their physicians during this study.

#### 11.4.7. Contraception Requirements

Patients should not become pregnant or father a child while on this study because the study treatments in this study can affect an unborn baby. Women should not breastfeed a baby while on this study. It is important that patients understand the need to use birth control while on this study. Female patients of childbearing potential must agree to use 2 methods of contraception (1 highly effective and 1 effective) and have a negative serum pregnancy test at Screening, and male patients must use an effective barrier method of contraception if sexually active with a female of childbearing potential.

Highly effective methods include:

1. Hormonal contraceptives (e.g., combined oral contraceptives, patch, vaginal ring, injectables, and implants)
2. Intrauterine device or intrauterine system

### 3. Vasectomy or tubal ligation

Effective methods include:

1. Barrier methods of contraception (e.g., male condom, female condom, cervical cap, diaphragm, and contraceptive sponge)

Of particular note,

- No barrier method by itself achieves a highly effective standard of contraception
- The proper use of diaphragm or cervical cap includes use of spermicide and is considered 1 barrier method.
- The cervical cap and contraceptive sponge are less effective in parous women.
- The use of spermicide alone is not considered a suitable barrier method for contraception.
- A combination of male condom with either cap, diaphragm or sponge with spermicide (double barrier methods) are also considered acceptable (i.e., effective), but not highly effective, birth control methods.
- Male and female condoms should not be used together as they can tear or become damaged.

Alternatively, the following fulfill the contraception requirements:

1. A sexual partner who is permanently surgically sterilized or post-menopausal.
2. Total (true) abstinence (when this is in line with the preferred and usual lifestyle of the patient) is an acceptable method of contraception. Note: Periodic abstinence (e.g., calendar, ovulation, symptothermal, and post-ovulation methods) and withdrawal are not acceptable methods of contraception.

The methods of acceptable contraception must be explained to both male and female potential patients. In order to be eligible for the study, patients must agree to use the methods of birth control described above throughout the study and for 3 months following the last dose of study treatment at the time of consent for the study.

Please see Section 4.4.1 for additional safety information related to pregnancy.

#### **11.4.8. Radiation Treatment**

If clinically indicated, palliative radiation therapy to non-target lesions is permitted but study drug should be held for  $\geq 1$  day before the start of palliative radiation therapy and  $\geq 1$  day following each dose of palliative radiation therapy. Treatment with selinexor shall not be discontinued solely due to palliative radiation.

#### **11.5. Treatment Compliance**

The Investigator or other study staff will supervise study drug treatment given in the clinic and instruct the patient on study medication self-administration.

Patients will be asked to bring their study medication container with them at each visit and compliance with protocol-defined study drug intake will be checked by pill count.

Compliance to study medication will be recorded by study personnel after discussion with the patient and drug accountability. Compliance to study medication will be assessed by the Investigator or delegate and recorded in source documents. The date will be recorded as per study drug schedule. The Investigator or the designee will account for the number of tablets dispensed against those returned by the patient. Any deviations and missed doses will be recorded in the eCRF and drug accountability logs for verification with the reasons.

The Investigator or designee will try to ensure complete compliance with the dosing schedule by providing timely instructions to the patients. In case of non-compliance, the patients will be instructed again.

## 12. ADVERSE EVENTS

An AE is defined as any undesired medical occurrence in a patient or clinical investigation patient receiving a pharmaceutical product regardless of a causal relationship with this treatment. An AE can therefore be any unfavorable sign and unintended sign (including an abnormal laboratory finding), symptom, or disease temporarily associated with the use of a study drug, whether or not related to the study drug.

Any treatment-emergent abnormal laboratory result or test result (e.g., PE, ECG, Echo, vitals, etc.), which is clinically significant, (i.e., meets one or more of the conditions listed below), should be recorded as a single diagnosis on the AE page in the eCRF:

1. Accompanied by clinical symptoms
2. Leading to a change in study medication (e.g., dose modification, interruption or permanent discontinuation)
3. Requiring a change in concomitant therapy (e.g., addition of, interruption of, discontinuation of, or any other change in a concomitant medication, therapy or treatment)

It is the responsibility of the Investigator to document all AEs that occur during the study. AE information will be elicited by asking the patient a non-leading question, for example, "Have you experienced any new or changed symptoms since we last asked/since your last visit?" AEs should be reported on the appropriate page of the eCRF.

AEs should be reported for their actual grade and duration.

The term "severe" is used to describe the intensity of an AE; the event itself could be of relatively minor clinical significance (e.g., 'severe' headache). This is not the same as "serious." Seriousness of AEs is based on the outcome of an AE and usually associated with events that pose a threat to a patient's life or functioning.

The severity of the AE will be graded according to the CTCAE Grading Scale (see the CTCAE web page at <http://ctep.cancer.gov> for details). For AEs not covered by CTCAE, the severity will be characterized as "mild," "moderate," or "severe" according to the following definitions:

- Mild events are usually transient and do not interfere with the patient's daily activities.
- Moderate events introduce a low level of inconvenience or concern to the patient and may interfere with daily activities.
- Severe events interrupt the patient's usual daily activities.

The Investigator will make a judgment regarding the AE's relationship to study drug, as outlined below in [Table 7](#).

**Table 7: Classification of Adverse Events by Causality**

Not related	The lack of a temporal relationship of the event to study treatment makes a causal relationship not reasonably possible, or by any other drugs, therapeutic interventions or underlying conditions that provide a sufficient explanation.
Related	The temporal relationship of the event to study treatment makes a definitive relationship, and the event is more likely explained by exposure to the study treatment than by any other drugs, therapeutic interventions or underlying conditions.

## 12.1. Serious Adverse Events

A serious adverse event (SAE) is any untoward medical occurrence that occurs at any dose (including after the ICF is signed and prior to dosing) that:

- Results in death
- Is life-threatening (patient is at immediate risk of death from the event as it occurred)
- Requires in-patient hospitalization (formal admission to a hospital for medical reasons) or prolongation of existing hospitalization
- Results in persistent or significant disability/incapacity
- Results in a congenital anomaly/birth defect

Important medical events that may not result in death, are not life-threatening, or do not require hospitalization may be considered SAEs when, based on appropriate medical judgment, they may jeopardize the patient and may require medical or surgical intervention to prevent one of the outcomes listed in this definition. Examples of such events include allergic bronchospasm requiring intensive treatment in an emergency room or at home, blood dyscrasias or convulsions that do not result in in-patient hospitalization, or the development of drug dependency or drug abuse.

Hospitalizations for elective surgery or other medical procedures that are not related to a treatment-emergent AE are not considered SAEs.

Progression of the malignancy (including fatal outcomes) should not be reported as an SAE during the study or within the safety reporting period (see below). Sudden and unexplained death should be reported as an SAE.

#### **12.1.1. AE and SAE Follow-up**

All AEs occurring during the study are to be followed up in accordance with good medical practice until they are resolved, stabilized or judged no longer clinically significant or, if a chronic condition, until fully characterized. Any AEs that are considered drug-related must be followed until resolution or until stabilization.

#### **12.1.2. Post-Study Adverse Events and Serious Adverse Events**

All unresolved AEs should be followed by the Investigator until the events are resolved, the patient is lost to follow-up, or the AE is otherwise explained. At the last scheduled visit, the Investigator should instruct each patient to report any subsequent event(s) that the patient, or the patient's personal physician, believes might reasonably be related to participation in this study.

Prior to the conclusion of the study at the site, the Investigator should notify the Karyopharm Pharmacovigilance Department (see Section 12.1.3.1) of any death or AE occurring at any time after a patient has discontinued or terminated study participation that may reasonably be related to this study.

After study conclusion, the Investigator should notify Karyopharm Therapeutics Inc., or its designee, of any death or AE he or she is aware of occurring at any time after a patient has discontinued or terminated study participation that may reasonably be related to this study. Karyopharm Therapeutics Inc. should also be notified if the Investigator should become aware of the development of cancer or of a congenital anomaly in a subsequently conceived offspring of a patient that has participated in this study.

#### **12.1.3. Serious Adverse Event Reporting**

##### **12.1.3.1. Reporting Requirements**

ALL SAEs occurring in any patient, must be reported to the Karyopharm Pharmacovigilance Department within 24 hours of first knowledge of the event by the principal investigator or assigned site personnel. The following information will be requested from the investigational site:

- Protocol number
- Site and/or investigator number
- Patient number
- Demographic data
- Brief description of the event
- Onset date and time
- Resolution date and time, if the event resolved

- Current status, if event not yet resolved
- Any concomitant treatment and medication
- Investigator's assessment of the SAE's relationship to investigational product
- Outcome of the event, if available

This information will be captured in the SAE report form and/or the study specific safety database and will be forwarded to:

- Pharmacovigilance Department
- Karyopharm Therapeutics Inc.
- Email: [[contact]](mailto:[contact])
- North American sites, Fax to US: [contact]  
European sites, Fax to Germany: [contact]

Suspected unexpected serious adverse reactions will be collected and reported to the competent authorities and relevant ethics committees in accordance with the FDA's "Safety Reporting Requirements for Investigational New Drugs and Bioanalytical/Bioequivalence Studies" or as per national regulatory requirements in participating countries.

All investigators participating in ongoing clinical studies with the study medication will receive copies of these reports for prompt submission to their Institutional Review Board (IRB) or Ethics committee (EC), as applicable. Reporting of SAEs by the Investigator to the IRB or EC will be done in accordance with the standard operating procedures and policies of the IRB/EC. Adequate documentation must be maintained showing that the IRB/EC was properly notified.

In addition, Karyopharm Therapeutics Inc. will communicate all cases of cerebellar toxicities of Grade 3 or higher to the regulatory authority, IRBs and investigators, in the format of an expedited Safety Report within 7 days of awareness of the event.

## **12.2. Overdose**

An overdose is defined as a deliberate or accidental administration of study medication to a study patient at a dose above that which is assigned to that individual patient according to the study protocol. In the event of drug overdose, the Investigator and Karyopharm Medical Monitor should be notified immediately and the patient observed closely for AEs. The patient should be treated symptomatically as appropriate, and the incident of overdose and related AEs and/or treatment documented in the patient's medical record. In addition to documenting the overdose in the patient's records, the overdose must be reported to Karyopharm Pharmacovigilance on an SAE report form. Any AE or SAE observed as a consequence of the overdose will be handled as described in Section 12.2, as appropriate.

As selinexor is metabolized by GSH conjugation, it is conceivable that hepatic GSH depletion can occur in case of overdose. Therefore, in patients who develop liver function test abnormalities, supportive measures such as SAM 400 mg orally 1-4 times a day, or other drugs that can replace GSH, should be considered.

Medication errors, and uses of the study medication outside what is foreseen in the protocol, including misuse and abuse of the product must also be reported to Karyopharm Pharmacovigilance on an SAE report form.

### **12.3. Pregnancies**

Pregnancy *per se* is not considered an AE unless there is cause to believe that the investigational drug may have interfered with the effectiveness of a contraceptive medication.

Each pregnancy in a patient or partner of a patient on selinexor must be reported to the Sponsor within 24 hours of learning of its occurrence. The pregnancy should be followed up to determine outcome, including spontaneous or voluntary termination, details of the birth, and the presence or absence of any birth defects, congenital abnormalities, or maternal and/or newborn complications. Follow-up and documentation must occur even if the patient withdraws from the study or the study is completed.

The avoidance of fathering a child is recommended for 3 months following the discontinuation of selinexor therapy. No information is currently available regarding the effects of selinexor on fertility, gestation or subsequent child development.

Any pregnancy within 3 months post-study should be reported to the study investigator and the sponsor's designee.

## **13. STATISTICAL METHODS**

### **13.1. General Considerations**

#### **13.1.1. Statistical and Analytical Plans**

This is a Phase 2b, single-arm, open-label, multicenter study of selinexor 80 mg with dexamethasone 20 mg (Sd), both given orally twice weekly for each week of four-week cycles, to patients with MM previously treated with lenalidomide, pomalidomide, bortezomib, carfilzomib, and daratumumab, and refractory to prior treatment with glucocorticoids, an immunomodulatory agent (IMiD), a proteasome inhibitor (PI), and the anti-CD38 mAb daratumumab.

This study consists of two parts and will enroll approximately 210 patients overall. Part 1 (protocol V1-3) enrolled patients with both penta-refractory MM and quad-refractory MM. Part 2 (protocol V $\geq$ 4.0) will enroll patients with penta-refractory MM only, but continue all patients enrolled in Part 1.

The population for the primary efficacy analysis will contain only patients with penta-refractory MM enrolled in Part 2. Efficacy results for patients with quad-refractory MM and patients with penta-refractory MM enrolled in Part 1 will be analyzed separately. Safety analyses will be performed on the overall population of patients who received any amount of study treatment, presented overall and by study part, and separately for Part 1 penta-refractory MM patients and quad-refractory MM patients.

Hypothesis testing will be used for the primary efficacy endpoint data, in order to evaluate if selinexor plus dexamethasone provides statistically significant improvement in efficacy over a minimally acceptable level of 10% ORR. No formal hypothesis-testing will be used for other study data, such as demographics and safety data.

Tabulations will be produced for appropriate disposition, demographic, baseline, efficacy and safety parameters. For categorical variables, summary tabulations of the number and percentage of patients within each category (with a category for missing data) of the parameter will be presented, as well as two-sided 95% confidence intervals (CI), unless otherwise stated. For continuous variables, the number of patients, mean, median, standard deviation (SD), minimum, and maximum values will be presented. Time-to-event data will be summarized using Kaplan-Meier (KM) methodology using 25th, 50th (median), and 75th percentiles with associated 2-sided 95% confidence intervals, as well as percentage of censored observations.

CCI [REDACTED]

[REDACTED]

[REDACTED]

[REDACTED]

[REDACTED]

[REDACTED]

### 13.1.3. Disposition of Patients

A tabulation of patient disposition will be presented, including the number in each analysis population, the number with non-evaluable disease according to the IMWG criteria, the number censored at each of the PFS and OS analyses, the number lost to follow-up, the number that withdrew prior to completing the study, and reason(s) for withdrawal. This tabulation will be presented separately for each study part and by quad-refractory MM and penta-refractory patient populations in Part 1.

#### **13.1.4. Blinding and Randomization**

This is an open-label, single-arm study, therefore blinding and randomization are not applicable.

#### **13.1.5. Dose Adjustment**

The dose level for an individual patient may be escalated, based on efficacy considerations, after a minimum of 2 cycles of study therapy. Reasons for dose escalation can include, for example, a response of SD or PR with acceptable safety. Dose reduction can take place, based on the guidelines in Section 11.1.5. CCI

[REDACTED]

### **13.2. Analysis Datasets**

#### **13.2.1. Populations to be Analyzed**

##### **13.2.1.1. Modified Intent-to-Treat (mITT) Population**

The modified intent-to-treat (mITT) population will consist of Part 2 patients with penta-refractory MM who met all eligibility criteria (or did not meet all eligibility criteria but received waiver from Sponsor to participate in the study), and received at least 1 dose of study treatment (partial or complete). This population will include patients who have discontinued therapy due to toxicity or disease progression and patients who have died from any cause, including those related to study drug or disease. This population (Part 2 patients with penta-refractory MM only) will be used for the primary analysis of efficacy.

##### **13.2.1.2. Per-Protocol Population**

A per-protocol (PP) population will consist of all patients in the mITT population who meet the following criteria:

- Have selinexor compliance  $\geq 70\%$ ,
- Have at least one adequate post-baseline response assessment unless died or withdrew from study before that.
- No major protocol violations that would compromise the assessment of efficacy. The list of major protocol violations that affect statistical analysis will be finalized before database lock.

Major violations will be determined independently of knowledge of response to therapy, prior to database lock and study analysis. This population will be used for supportive inferences concerning efficacy, however, if there are major differences between the results in this population and those obtained in the mITT population, this will be taken into consideration in the assessment of efficacy.

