#### Synopsis

- Objectives: updated for consistency with the Statistical Analysis Plan:
  - Updated definitions of Durations of CBR and DCR.  
CCI [REDACTED]
- Statistical Methods: updated the definition of mITT and PP populations, for consistency with SAP, CCI [REDACTED].

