1.7. MODIFICATIONS TO THE STATISTICAL SECTION OF THE PROTOCOL

The current SAP is based on Protocol v5.0. The following modifications were made to the statistical section of protocol.

Analysis Populations

- Additional analysis populations for efficacy endpoints and additional safety populations (Sections 3.1.1, 3.1.2, and 3.1.3) are defined to present data in a comprehensive manner.
- The definition of the modified intent-to-treatment (mITT) population is revised to include patients who did not meet all eligibility criteria but received Sponsor waiver to participate in the study. Waivers are not granted to patients who do not meet key eligibility criteria such as required prior therapies and measurable disease at baseline.
- The definition of the per-protocol population is revised (Section 3.1.1). The requirement of having completed at least one cycle of treatment is removed. Instead, patients are required to have at least one adequate post-baseline response assessment unless they died or withdrew from the study before that. Moreover, patients are required to have a compliance rate of at least 70% of selinexor instead of 80%.

Secondary Efficacy Endpoints

- The censoring rules for the secondary endpoints of duration of clinical benefits is revised to follow the TTP rule, such that it is consistent with the censoring rule for duration of response.
- The endpoint of duration of disease control is removed.

- The secondary endpoint of TTNT is added.

CCI [REDACTED]

- [REDACTED]
[REDACTED]
[REDACTED]

CCI [REDACTED]

- [REDACTED]
[REDACTED]
- [REDACTED]

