3.1.1. Efficacy Populations

The primary efficacy populations will only include patients from Part 2. Results for Part 1 patients will be summarized and analyzed separately.

The ***modified intent-to-treat (mITT) population*** will consist of Part 2 patients with penta-refractory MM who met all eligibility criteria (or did not meet all eligibility criteria but received waiver from Sponsor to enter the study), and received at least one dose of study treatment (partial or complete). This population will include patients who have discontinued therapy due to toxicity or PD and patients who have died from any cause, including those related to study treatment or disease. The mITT population will be used for the primary efficacy analyses.

The ***BCLPD-ref population*** will consist of patients in Part 2 who had MM *documented* to be refractory to bortezomib, carfilzomib, lenalidomide, pomalidomide, and daratumumab, and received at least one dose of study treatment (partial or complete).

The ***CLPD-ref population*** will consist of patients in Part 2 who had MM *documented* to be refractory to carfilzomib, lenalidomide, pomalidomide, and daratumumab, and received at least one dose of study treatment (partial or complete).

The **BCPD-ref population** will consist of patients in Part 2 who had MM *documented* to be refractory to bortezomib, carfilzomib, pomalidomide, and daratumumab, and received at least one dose of study treatment (partial or complete).

The **CPD-ref population** will consist of patients in Part 2 who had MM *documented* to be refractory to carfilzomib, pomalidomide, and daratumumab, and received at least one dose of study treatment (partial or complete). Note that this population has MM that is refractory to both second generation IMiDs (pomalidomide) and proteasome inhibitor (carfilzomib), as well as daratumumab.

The BCLPD-ref, CLPD-ref, BCPD-ref, CPD-ref populations will be used for supportive inferences concerning efficacy.

A patient is claimed to have documented refractory to a therapy if one of the following criteria is met:

- Best response on the therapy is SD or worse
- Patient progressed or relapsed during treatment
- Patient progressed or relapsed within 60 days after discontinuing this therapy.

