3.1.3. Additional Analysis Populations

Analysis of selected efficacy endpoints will be conducted in the following populations respectively:

The **All Penta-ref** population will consist of all patients from mITT (Part 2) and all Part 1 patients with penta-refractory MM who met all eligibility criteria (or did not meet all eligibility criteria but received waiver from Sponsor to enter the study), and received at least one dose of study treatment (partial or complete).

The **high-risk population** will consist of all Part 2 patients with penta-refractory MM with any of the following high-risk chromosomal abnormalities including del (17p)/p53, t(14; 16), t(4; 14), and 1q21, and received at least one dose of study treatment (partial or complete).

Chromosomal abnormalities are determined by the FISH test. If adequate test results from a central laboratory are available, such results will be used to determine the chromosomal abnormality status; otherwise, test results from the local site's laboratory will be used. If local laboratory results are not available either, FISH results from initial diagnosis (Disease History eCRF page) will be used if available. In the absence of test results indicating abnormality, a patient will be classified as normal for the corresponding mutation.

The ***Efficacy-Evaluable (EE) population*** will consist of all patients in the mITT population with at least one adequate post-baseline IRC-based MM response assessment.

The ***per-protocol (PP) population*** will consist of all patients in the mITT population who meet the following criteria:

- Have selinexor compliance $\geq 70\%$, see Section 3.4.2 for the definition of selinexor compliance rate.
- Have at least one adequate post-baseline response assessment unless died or withdrew from study before that.

The ***Part 1 quad-ref MM population*** (Part 1 – Quad) will consist of all quad-refractory patients in Part 1 who received at least one dose of study treatment (partial or complete).

The ***Part 1 penta-ref MM population*** (Part 1 – Penta) will consist of all penta-refractory patients in Part 1 who received at least one dose of study treatment (partial or complete).

Selected safety endpoints will be summarized within the Part 1 - Quad and Part 1 - Penta, populations respectively.

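### The SAP's per-protocol set omits the protocol's exclusion of major protocol violators, and the omission is not declared

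*Protocol*

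**What the plan says.** Protocol 13.2.1.2, repeated in the synopsis under Statistical Methods, builds the PP set from mITT patients who meet three criteria. The third is "No major protocol violations that would compromise the assessment of efficacy". The same section adds a safeguard: "Major violations will be determined independently of knowledge of response to therapy, prior to database lock and study analysis". It makes PP supportive, but says that a major difference between the PP and mITT results will be weighed when efficacy is judged.

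SAP 3.1.3 also builds PP from mITT, but with two bullets. The first is selinexor compliance of at least 70% ("see Section 3.4.2 for the definition of selinexor compliance rate"). The second is "Have at least one adequate post-baseline response assessment unless died or withdrew from study before that". No third bullet follows.

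SAP 1.7 states "The current SAP is based on Protocol v5.0" and lists what it changes. For PP it says "The requirement of having completed at least one cycle of treatment is removed", puts the assessment requirement in its place, and lowers the compliance limit from 80% to 70%. It says nothing about protocol violations, and neither does the visible text of SAP 1.8. The protocol's change log for version 6.0 says of the synopsis: "updated the definition of mITT and PP populations, for consistency with SAP".

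**The concern.** Two documents in force define the same analysis set differently, and the reader is not told. A programmer who follows the SAP will keep in PP any patient with a violation serious enough to compromise the efficacy assessment, provided that the compliance and assessment criteria are met. The purpose of a PP analysis is to show whether the mITT result survives removal of such patients. The protocol gives that comparison a role in judging efficacy, so the definition should be settled before results are seen. This matters more in an open-label, single-arm trial, where site and sponsor staff can see responses as they accrue.

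**Working it through.** The plan states no figure on this point, so the check is a comparison of texts.

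**1. The two definitions side by side**

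| Criterion | Protocol 13.2.1.2 and synopsis | SAP 3.1.3 |
|---|---|---|
| Selinexor compliance of at least 70% | Present | Present |
| Adequate post-baseline response assessment, with an exemption for death or withdrawal | Present | Present |
| No efficacy-compromising major violation | Present | Absent |

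**2. Is the difference declared?** Start from the PP definition that preceded the SAP. The protocol's version 4.0 change log describes it as at least one completed cycle plus no major violation. SAP 1.7 shows that the compliance limit was then 80%. The visible log entries for versions 4.1 and 5.0 record no change to it. Now apply the changes that SAP 1.7 declares:

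- Before: compliance of at least 80%; one cycle completed; no major violation.
- Declared changes: 80% becomes 70%; the one-cycle rule becomes the assessment rule.
- After: compliance of at least 70%; assessment rule; no major violation.

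The outcome is the version 6.0 protocol definition, not the one in SAP 3.1.3. The SAP's own list of changes therefore does not lead to the SAP's own PP set.

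**3. Does another visible SAP rule do the same job?** The mITT definition in SAP 3.1.1 covers eligibility (or a waiver) and one dose. The efficacy-evaluable set adds an adequate assessment by the independent review committee. The compliance rate in SAP 3.4.2 leaves out of its denominator doses missed through interruption or for other reasons that were not the patient's choice. None of these removes a patient for a conduct violation other than low compliance.

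**4. Where is PP used?** SAP section 4 repeats ORR, DOR, CBR and duration of clinical benefit in the additional populations, which include PP. Protocol 13.3.4 plans the secondary efficacy endpoints in both mITT and PP.

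**5. Timing.** The protocol says the violation list will be finalised before database lock. SAP 1.6 runs the primary analysis on a database snapshot once all patients have completed their Cycle 2 myeloma assessments, and places the formal lock at the end of the study. A list tied only to lock could be completed after the primary results are known.

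**6. Size.** Suppose the SAP's PP set has *n* patients and *r* responders, and *V* of those patients are major violators, of whom *s* responded. The SAP gives ORR = *r*/*n*. The protocol gives (*r* − *s*)/(*n* − *V*). The protocol's figure is lower when *s*/*V* exceeds *r*/*n* and higher when it is below. Neither *V* nor *s* is in the documents, so both the size and the direction of the difference are unknown.

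**The case against.** The best defence is that PP is only supportive, that the mismatch is one line, and that it could be resolved in either direction, since the SAP was written against version 5.0 and the protocol was later aligned to it. The first two parts stand and limit the seriousness. The third affects the choice of remedy, not whether the texts conflict. The version 6.0 alignment kept the criterion in both places, which makes an oversight in the SAP the likelier explanation, though this is an inference. It can also be said that the protocol's safeguard already requires violations to be settled before study analysis, which would cover the snapshot. That is a fair reading, but the sentence on finalising the list mentions lock alone, and the SAP carries neither the criterion nor the safeguard.

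A reader might infer four stronger things that the documents do not support.

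- *No supportive analysis removes violators.* The list of supportive ORR analyses in SAP 4.1.3 is redacted, so this cannot be known. Some departures are removed in any case: ineligible patients without a waiver are outside mITT, and those below 70% selinexor compliance are outside PP.
- *The omission is what keeps waived patients in PP.* Both documents draw PP from an mITT set that admits patients who "did not meet all eligibility criteria but received waiver from Sponsor to enter the study" (SAP 3.1.1; the protocol's wording is equivalent). The protocol does not call a waived eligibility failure a major violation, and SAP 1.7 bars waivers for key criteria such as required prior therapy and measurable disease.
- *The SAP's PP set is nearly mITT.* The two remaining criteria still exclude patients, and no counts are given.
- *A few violators could tip the trial result.* With 122 patients, 20 responders give an exact lower limit of 10.31%, and removing one responding violator gives 19/121, lower limit 9.73%. But the 10% rule in Protocol 13.3.3 and SAP 4.1.2 applies to mITT only. PP membership cannot alter it, and no PP threshold is stated.

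**Conclusion.** Wrong as written, but minor. The PP definitions in the two documents differ by one criterion, and the SAP does not declare the difference. Followed literally, the SAP keeps efficacy-compromising violators in PP and weakens a comparison on which the protocol says it will draw. The primary ORR test, its 10% threshold and the sample size are untouched. The effect on the PP estimates cannot be quantified, because the number of violators and their responses are not given. The conclusion rests on the visible text. It assumes that no redacted passage restores the criterion, and the reconstruction of the earlier PP definition relies on the change log because the version 5.0 text is not available. How waived patients should be classed is only a point to clarify.

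**What to change.** - Add the third criterion to SAP 3.1.3 in the protocol's terms. Also correct the pointer in SAP 1.7, which sends the reader to SAP 3.1.1 for a PP definition that stands in 3.1.3.
- State in the SAP that the violation list is finalised, without knowledge of response, before the primary-analysis database snapshot, not only before the formal lock at the end of the study.
- Say in one sentence whether a waived eligibility failure can count as a major violation.
- If the removal was intended, delete the criterion from Protocol 13.2.1.2 and the synopsis instead, and declare and justify the change in SAP 1.7.

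The first route costs one bullet and a timing sentence. The list is already required by the protocol, and the PP set may become somewhat smaller. The second route needs a protocol amendment and gives up the violator-free comparison. Neither changes the primary analysis.
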